### 12.2.1.2 Immediate action: determination of IMP discontinuation

All PDILI events require immediate action, testing, and monitoring.

The immediate action is dependent on the laboratory values and symptoms of hepatitis or hypersensitivity and ranges from continuation of IMP (followed by immediate investigation) to immediate and permanent discontinuation (see [Section 6.5.1](#) and [Table 12-3](#) for details).

When IMP is discontinued, all concomitant medications and herbal supplements that are not medically necessary should also be discontinued. The Investigator should also consider dose reduction for medically necessary concomitant medication and consider changing any medically required concomitant medication known to be hepatotoxic to a suitable alternative.

#### 12.2.1.2.1 IMP restart/rechallenge

Subjects who are immediately discontinued from IMP due to having met certain criteria for PDILI (as described in [Section 6.5.1](#) and [Table 12-3](#)), but for whom an alternative diagnosis is confirmed, ie, drug-induced liver injury is excluded, can rarely restart IMP.

Rechallenge with IMP can occur only if ALL of the following requirements are met at the time of the rechallenge.

- The results of additional testing and monitoring described in [Section 12.2.1.3](#) and [Section 12.2.1.4](#) confirm a nondrug-related cause for the abnormal hepatic laboratory parameters and any associated symptoms (ie, a subsequent alternative diagnosis fully explains the hepatic findings).
- The subject has shown clear therapeutic benefit from the IMP.
- Subject's ALT or AST elevations do not exceed  $\geq 5xULN$ .
- Subject's total bilirubin is  $< 2xULN$ .
- Subject has no signs or symptoms of hypersensitivity or hepatitis.
- During the double-blind Treatment Period, the rechallenge is approved by the UCB responsible physician, DMC, and a hepatologist.
- During the OLE and OLE2 Periods, the rechallenge is approved by the UCB responsible physician.
- Subject agrees to the Investigator-recommended monitoring plan.

---

### 12.2.1.3 Testing: identification/exclusion of alternative etiology

The measurements and additional information required for the assessment of PDILI events when there is a reasonable possibility that they may have been caused by the IMP are detailed in [Table 12-4](#) (laboratory measurements) and [Table 12-5](#) (additional information). Results of the laboratory measurements and information collected are to be submitted to the sponsor on the corresponding eCRF. If the medical history of the subject indicates a requirement for other assessments not included below, these additional assessments should be completed and submitted, as applicable.

All blood samples should be stored, if possible. If tests are done locally for more rapid results, a concurrent sample must also be sent to the central laboratory.

The following measurements are to be assessed:

PUBLIC COPY  
This document cannot be used to support any marketing authorization application and any extensions or variations thereof.

**Table 12–4: PDILI laboratory measurements**

|                         |  |
|-------------------------|--|
| Virology-related | Hepatitis A IgM antibody   |
|                         | HBsAg  |
|                         | Hepatitis E IgM antibody   |
|                         | HBcAb-IgM  |
|                         | Hepatitis C RNA  |
|                         | Cytomegalovirus IgM antibody   |
|                         | Epstein-Barr viral capsid antigen IgM antibody (if unavailable, obtain heterophile antibody or monospot testing) |
| Immunology       | Anti-nuclear antibody (qualitative and quantitative)   |
|                         | Anti-smooth muscle antibody (qualitative and quantitative)   |
|                         | Type 1 anti-liver kidney microsomal antibodies (qualitative and quantitative)                                    |
| Hematology       | Eosinophil count   |
| Urinalysis       | Urine drug screen a   |
| Chemistry        | Amylase  |
|                         | Sodium, potassium, chloride, glucose, BUN, creatinine  |
|                         | Total bilirubin, ALP, AST, ALT, GGT, total cholesterol, albumin  |
|                         | If total bilirubin $\geq 1.5 \times \text{ULN}$ , obtain fractionated bilirubin to obtain % direct bilirubin     |
|                         | Serum CPK and LDH to evaluate possible muscle injury causing transaminase elevation                              |
| Additional       | Prothrombin time/INR b  |
|                         | Serum pregnancy test c  |
|                         | PK   |

ALP=alkaline phosphatase; ALT=alanine aminotransferase; AST=aspartate aminotransferase; BUN=blood urea nitrogen; CPK=creatine phosphokinase; GGT=gamma glutamyltransferase; HBcAb-IgM=hepatitis B core antibody-IgM; HBsAg=hepatitis B surface antigen; IgM=immunoglobulin M; INR=international normalized ratio; LDH=lactate dehydrogenase; PDILI=potential drug-induced liver injury; PK=pharmacokinetic; RNA=ribonucleic acid; ULN=upper limit of normal

a Tests in addition to the specified analytes may be performed based on the Investigator's medical judgment and subject history.

b Measured only for subjects with ALT  $> 8 \times \text{ULN}$ , elevations in total bilirubin, and symptoms of hepatitis or hypersensitivity. Hepatitis symptoms include fatigue, nausea, vomiting, and right upper quadrant pain or tenderness; hypersensitivity symptoms include eosinophilia ( $> 5\%$ ), rash, and fever (without clear alternative cause).

c For women of childbearing potential.

The following additional information is to be collected:

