### 6.5.1 Potential drug-induced liver injury IMP discontinuation criteria

Subjects with potential drug-induced liver injury (PDILI) must be assessed to determine if IMP must be discontinued. In addition, all concomitant medications and herbal supplements that are not medically necessary should also be discontinued.

The PDILI criteria below require immediate and permanent discontinuation of IMP for subjects with either of the following:

- ALT or AST  $\geq 8$ xULN
- ALT or AST  $\geq 3$ xULN and coexisting total bilirubin  $\geq 2$ xULN

The PDILI criterion below requires immediate discontinuation of IMP for:

- Subjects with ALT or AST  $\geq 3 \times \text{ULN}$  who exhibit temporally associated symptoms of hepatitis or hypersensitivity. Hepatitis symptoms include fatigue, nausea, vomiting, right upper quadrant pain or tenderness. Hypersensitivity symptoms include fever (without clear alternative cause), rash, or eosinophilia (ie,  $>5\%$ ).

If a nondrug-related cause for the symptoms can be confirmed, these subjects may resume IMP administration after discussion with the responsible UCB physician, but only when the requirements for rechallenge with IMP as provided in [Section 12.2.1.2.1](#) are followed.

The PDILI criterion below allows for subjects to continue on IMP at the discretion of the Investigator.

- Subjects with ALT or AST  $\geq 5 \times \text{ULN}$  and  $< 8 \times \text{ULN}$ , total bilirubin  $< 2 \times \text{ULN}$ , and no eosinophilia (ie,  $\leq 5\%$ ), with no fever, rash, or symptoms of hepatitis (eg, fatigue, nausea, vomiting, right upper quadrant pain or tenderness).

Evaluation of PDILI must be initiated as described in [Section 12.2.1](#) with repeat tests performed in two weeks. Upon re-test, if ALT or AST values have reduced to  $< 5 \times \text{ULN}$ , the subject can continue with the study. However, if ALT or AST remains  $\geq 5 \times \text{ULN}$  and  $< 8 \times \text{ULN}$  after re-test, IMP should be temporarily withheld and subject should undergo a repeat test in two weeks. If ALT or AST values remain  $\geq 5 \times \text{ULN}$  even after the second re-test, then the subject should be permanently withdrawn from the study and should be followed for possible drug-induced liver injury.

If subjects are unable to comply with the applicable monitoring schedule, IMP must be discontinued immediately.

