**Table 12-3: Required investigations and follow up for PDILI**

| Laboratory value  |                     | Symptoms a of hepatitis or hypersensitivity |     | Immediate  |   | Follow up   |  |
|-------------------|---------------------|--|-----|--|---|---|--|
| ALT or AST        | Total bilirubin     | NA   | Yes | Consultation requirements  | Actions   | Testing   | Evaluation   |
| ≥3xULN            | ≥2xULN b | NA   | Yes | Hepatology consult c
Medical Monitor must be notified within 24 hours (eg, by laboratory alert) and subject discussed with Medical Monitor ASAP.     | Immediate, permanent IMP discontinuation. e  | Essential: Must have repeat liver chemistry values and additional testing completed ASAP (see Section 12.2.1.3); recommended to occur at the site with HCP.               | Monitoring of liver chemistry values at least twice per week until values normalize, stabilize, or return to within baseline values. d  |
| ≥8xULN            | NA                  | NA   | NA  | Hepatology consult.
Medical Monitor must be notified within 24 hours (eg, by laboratory alert) and subject discussed with Medical Monitor ASAP.                 | Immediate, permanent IMP discontinuation.   |   |  |
| ≥5xULN and <8xULN | <2xULN              | No   | No  | Discussion with Medical Monitor required.
Consider need for hepatology consult if there is no evidence of resolution (see Follow up requirements). e | Further investigation – immediate IMP discontinuation not required (see Section 12.2.1.2).

IMP discontinuation required if any of the following occur:
Subject cannot comply with monitoring schedule.
Liver chemistry values continue to increase
Liver chemistry values remain ≥5xULN after | Essential: Every attempt must be made to have repeat liver chemistry values and additional testing completed within 48 hours at the site with HCP (see Section 12.2.1.3). | Monitoring of liver chemistry values at least twice per week for 2 weeks. d 
 
Immediate IMP discontinuation required if liver chemistry values continue to increase.
 
 After 2 weeks of monitoring liver chemistry values: 
 
ALT or AST remains ≥5xULN <8xULN, IMP should be temporarily withheld and subject should undergo repeat test in 2 weeks.
 
 |

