**Table 12-3: Required investigations and follow up for PDILI**

| Laboratory value |                 | Immediate  |                           | Follow up  |         |  |
|------------------|-----------------|--|---------------------------|--|---------|--|
| ALT or AST       | Total bilirubin | Symptoms a of hepatitis or hypersensitivity | Consultation requirements | Actions  | Testing | Evaluation   |
|                  |                 |  |                           | 4 weeks of monitoring without evidence of resolution |         | Continue IMP if ALT or AST values <5xULN; continue to monitor at least twice per week until values normalize, stabilize, or return to within Baseline values.
If ALT or AST remains ≥5xULN after second re-test, immediate, permanent IMP discontinuation required.

Continue to monitor until values normalize, stabilize, or return to within baseline values. d |

ALP=alkaline phosphatase; ALT=alanine aminotransferase; ASAP=as soon as possible; AST=aspartate aminotransferase; HCP=healthcare practitioner; IMP=investigational medicinal product; NA=not applicable; PDILI=potential drug-induced liver injury; ULN=upper limit of normal

a Hepatitis symptoms include fatigue, nausea, vomiting, and right upper quadrant pain or tenderness; hypersensitivity symptoms include eosinophilia (>5%), rash, and fever (without clear alternative cause)

b If the subject also has ≥2xULN ALP, the possibility of an indication of biliary obstruction should be discussed with the Medical Monitor.

c Details provided in Section 12.2.1.1. The local hepatologist is the expert usually consulted by the treating physician for assessment and management of potential hepatic disease. This would usually be a hepatologist, but may be a gastroenterologist.

d Unless an alternative monitoring schedule is agreed by the Investigator and UCB responsible physician. Determination of stabilization is at the discretion of the Investigator in consultation with the hepatologist (as applicable) and UCB responsible physician, as needed.

e Details provided in Section 12.2.1.2.1.

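### Table 12-4 footnote b, read literally, mandates prothrombin time/INR only when ALT >8xULN, raised bilirubin and symptoms coincide; an asymptomatic potential Hy's Law case has no mandated INR, and gaps remain even if the three items are alternatives

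*Protocol*

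**What the plan says.** Section 12.2.1.3 presents Table 12-4 as the laboratory work-up for PDILI events. Table 12-3 ties its rows to that section; for the most serious rows it states "Essential: Must have repeat liver chemistry values and additional testing completed ASAP". Prothrombin time/INR appears once in Table 12-4, under the additional tests, and carries footnote b. The footnote limits the test to subjects with ALT >8xULN, "elevations in total bilirubin, and symptoms of hepatitis or hypersensitivity". It names ALT and not AST, uses a strict inequality, and gives no bilirubin cut-off. The routine panel in Table 12-2 contains no INR.

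Section 6.5.1 sets the stopping rules.

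- Its first criteria "require immediate and permanent discontinuation of IMP for subjects with either of the following": ALT or AST ≥8xULN; or ALT or AST ≥3xULN with total bilirubin ≥2xULN.
- It also requires an immediate stop for subjects with ALT or AST ≥3xULN "who exhibit temporally associated symptoms of hepatitis or hypersensitivity".
- In the 5 to <8xULN class (bilirubin <2xULN, no symptoms), if values stay ≥5xULN "even after the second re-test, then the subject should be permanently withdrawn from the study and should be followed for possible drug-induced liver injury". Table 12-3 agrees ("after second re-test, immediate, permanent IMP discontinuation required") and adds a further route: "Immediate IMP discontinuation required if liver chemistry values continue to increase".

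Section 12.1.1.3 defines potential Hy's Law as ALT or AST ≥3xULN with bilirubin ≥2xULN, without ALP ≥2xULN and without another explanation. Neither symptoms nor an 8xULN threshold is part of that definition.

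**The concern.** The INR trigger matches none of the liver classes that the protocol itself treats as serious. Each stopping rule refers to ALT or AST and uses ≥; the footnote refers to ALT and uses >. The stopping rules treat bilirubin and symptoms as separate routes; the footnote joins them to the ALT condition. A site that follows the text would omit INR in a case that must be reported as an adverse event of special interest, while a site using clinical judgement would obtain it. At stake is a uniform mandated work-up for the trial's most serious liver events, whose Table 12-4 results go to the eCRF.

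**Working it through.** The protocol states no figure for this point, so there is nothing to reproduce. The check is one of logical coverage.

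**Inputs.** The footnote trigger comes from Table 12-4, the stop classes from Section 6.5.1 and Table 12-3, and Hy's Law from Section 12.1.1.3. One assumption is needed: raised bilirubin means >ULN, because the footnote gives no threshold.

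**Grid.** ALT and AST each take five levels in multiples of ULN (<3, 3 to <5, 5 to <8, exactly 8, >8). Bilirubin takes three (≤ULN, >ULN to <2xULN, ≥2xULN), and symptoms are absent or present. That gives 5 × 5 × 3 × 2 = 150 combinations.

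**Class sizes.**
- ALT or AST ≥8xULN: (25 − 9) × 3 × 2 = 96.
- ALT or AST ≥3xULN with bilirubin ≥2xULN: (25 − 1) × 1 × 2 = 48.
- ALT or AST ≥3xULN with symptoms: (25 − 1) × 3 × 1 = 72.
- 5 to <8xULN, bilirubin <2xULN, no symptoms: (9 − 4) × 2 × 1 = 10.

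**Literal reading** (ALT >8 and bilirubin >ULN and symptoms):
- ≥8xULN: 5 AST levels × 2 bilirubin levels × 1 = 10.
- Bilirubin class: 5 × 1 × 1 = 5.
- Symptom class: 5 × 2 × 1 = 10.
- 5 to <8xULN class: 0, by definition.

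**Alternatives reading** (any one of the three). A combination is missed only if ALT ≤8xULN, bilirubin is normal and there are no symptoms.
- ≥8xULN: missed are 3 ALT levels below 8 × 2 AST levels at or above 8 = 6, plus ALT exactly 8 with any of 5 AST levels = 5. Covered: 96 − 11 = 85.
- Bilirubin and symptom classes: all covered.
- 5 to <8xULN class: the 5 with raised bilirubin are covered and the 5 with normal bilirubin are not.

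| Class | Literal | Alternatives |
|---|---|---|
| ALT or AST ≥8xULN | 10 of 96 | 85 of 96 |
| ≥3xULN with bilirubin ≥2xULN | 5 of 48 | 48 of 48 |
| ≥3xULN with symptoms | 10 of 72 | 72 of 72 |
| 5 to <8xULN (re-test class) | 0 of 10 | 5 of 10 |

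Potential Hy's Law has the same coverage as the bilirubin class, because ALP does not enter the footnote.

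**Sensitivity to the bilirubin assumption.** If raised meant ≥2xULN, the literal counts become 5 of 96, 5 of 48, 5 of 72 and 0 of 10. On the alternatives reading the ≥8xULN class misses 11 × 2 = 22, leaving 74 of 96; the bilirubin and symptom classes stay complete, and the re-test class falls to 0 of 10.

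**Second grid.** A finer grid (ten ALT values, ten AST values, five bilirubin values, two symptom states, two ALP values) gives, in the table's order, 160 of 1020, 80 of 768, 160 of 960 and 0 of 198 on the literal reading, and 40 of 384 for Hy's Law. As alternatives it gives 958 of 1020, 768 of 768, 960 of 960, 132 of 198 and, for Hy's Law, 384 of 384. The fractions change with the grid. Which classes are incomplete does not.

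**Two concrete cases.** ALT 5xULN, bilirubin 3xULN, no symptoms: INR is not mandated literally, but is if the items are alternatives. AST 10xULN, ALT 6xULN, normal bilirubin, no symptoms: an immediate permanent stop, with no mandated INR on either reading.

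**The case against.** The strongest reply is that nothing in the protocol promises an INR with every stop. Table 12-3 sends sites to Section 12.2.1.3, which includes the footnote, so the two fit together and the limit may be deliberate. This stands in part: a reader might infer that the sections contradict each other, and they do not. The point is that the stated trigger is badly matched to the protocol's own classes.

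A reader might also infer that a Hy's Law case would go without INR in practice, or that subjects would be dosed, stopped or reported differently. The documents support neither. The footnote defines what is mandated and does not forbid the test. Section 12.2.1 allows further investigation, and Section 8.8 allows any needed assessment at an unscheduled visit. For the serious rows Table 12-3 states: "Medical Monitor must be notified within 24 hours (eg, by laboratory alert) and subject discussed with Medical Monitor ASAP". It requires a hepatology consult for the bilirubin and ≥8xULN classes and apparently also for the symptom class; the table is broken in this copy, but its layout suggests a shared cell. Stopping (Section 6.5.1), Hy's Law reporting (Section 12.1.1.3) and rechallenge (Section 12.2.1.2.1) do not use INR.

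The sponsor may have meant the three items as alternatives. That would remove the Hy's Law example but not the AST-only, exactly-8xULN and re-test gaps. In the 5 to <8xULN class a hepatology consult is only to be considered. Finally, the grid counts carry limited information: 5 of the 11 missed combinations come from one boundary value, and the 0 of 10 follows from how that class is defined.

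**Conclusion.** The point holds as a wording defect in a current safety procedure. Read literally, footnote b fully covers no Section 6.5.1 stop route and does not fully cover potential Hy's Law. Read as alternatives, it still misses AST ≥8xULN with ALT ≤8xULN, ALT exactly 8xULN, and the second re-test stop, in each case when bilirubin is normal and there are no symptoms. The conclusion rests on the text and does not depend on the assumed bilirubin cut-off.

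The consequence is modest: whether INR is obtained in comparable serious liver events may differ between sites. No efficacy estimate, stopping decision or reporting duty changes. The protocol gives no expected number of such events, so the number of affected subjects cannot be stated, and the grid fractions must not be read as one. The footnote should be corrected because two readings are possible and neither is complete.

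**What to change.** Reword footnote b along these lines, keeping its existing definition of symptoms:

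*Measured for subjects with a PDILI event who have any of: ALT or AST ≥8xULN; total bilirubin >ULN; hepatitis or hypersensitivity symptoms; or IMP discontinued because ALT or AST in the 5 to <8xULN class keeps rising or is still ≥5xULN at the second re-test.*

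This reaches all 96, 48 and 72 combinations in the first three classes, both stop routes in the 5 to <8xULN class, and potential Hy's Law. For PDILI events it withdraws no INR that either reading of the present text mandates. Keeping >ULN as the bilirubin condition matters here: a ≥2xULN cut-off would drop INR for a subject with ALT 6xULN and bilirubin 1.8xULN, who is covered if the present items are alternatives. INR stays unmandated in the 5 to <8xULN class while bilirubin is normal and no stop route has been reached, so the footnote still limits testing. The cost is one footnote and a few additional INR measurements; the test is already in the panel.

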**Table 12–5: PDILI information to be collected**

|  |
|--|
| New or updated information  |
| Concomitant prescription and over-the-counter medications (eg, acetaminophen, herbal remedies, vitamins); dosages and dates should be included.  |
| Pertinent medical history, including the following: 
 
• History of liver disease (eg, autoimmune hepatitis, nonalcoholic steatohepatitis or other “fatty liver disease”)
 
• Adverse reactions to drugs
 
• Allergies
 
• Relevant family history or inheritable disorders (eg, Gilbert’s syndrome, alpha-1 antitrypsin deficiency)
 
• Recent travel
 
 Progression of malignancy involving the liver (Note: Metastatic disease to the liver, by itself, should not be used as an explanation for significant AST and/or ALT elevations) |
| The appearance or worsening of clinical symptoms of hepatitis or hypersensitivity (eg, fatigue, nausea, vomiting, right upper quadrant pain or tenderness, decreased appetite, abdominal pain, jaundice, fever, or rash)   |
| Recent clinically significant hypotension or hypoxemia with compromised cardiopulmonary function   |
| Alcohol and illicit drug use   |
| Results of liver imaging or liver biopsy, if done  |
| Results of any specialist or hepatology consult, if done   |
| Any postmortem/pathology reports   |

ALT=alanine aminotransferase; AST=aspartate aminotransferase; PDILI=potential drug-induced liver injury

#### 12.2.1.4 Follow-up evaluation

Potential drug-induced liver injury events require follow-up monitoring as described in [Table 12–3](#). Monitoring should continue until liver chemistry values normalize, stabilize, or return to baseline. Determination of stabilization is at the discretion of the Investigator in consultation with the hepatologist (as applicable) and UCB responsible physician, as needed.

### 12.3 Other safety measurements

#### 12.3.1 Assessment and management of TB and TB risk factors

All subjects will be assessed for TB at Screening and at the time points specified in the Schedule of Assessments ([Table 5–1](#), [Table 5–2](#), and [Table 5-3](#)) through physical examination for signs and symptoms of TB, chest x-ray ([Section 12.3.1.2](#)), laboratory testing ([Section 12.3.1.1](#)), and subject questionnaire ([Section 12.3.1.3](#)).

[figure not shown]
For the purposes of this study, TB definitions are as follows:

- c. Known TB infection:
  - Active TB infection or clinical signs and symptoms suspicious for TB (pulmonary or extra-pulmonary).

- 
- History of active TB infection involving any organ system or findings in other organ systems consistent with TB infection, unless adequately treated and proven to be fully recovered upon consult with a TB specialist.
  - Any evidence by radiography or other imaging modalities consistent with previously active TB infection that is not reported in the subject's medical history.
- d. High risk of acquiring TB infection:
- Known close exposure to another person with active TB infection within the 3 months prior to Screening.
  - Time spent in a healthcare delivery setting or institution where individuals infected with TB are housed and where the risk of transmission of infection is high.
- e. Latent TB infection (unless appropriate prophylaxis is initiated at least 8 weeks prior to IMP dosing and continued to completion of prophylaxis):
- The absence of signs, symptoms, or physical findings suggestive of TB infection with a positive IGRA test (or 2 indeterminate IGRA test results) and a chest x-ray (or other imaging) without evidence of TB infection. If the result of the IGRA test is indeterminate, the particular IGRA test previously performed may be repeated once; if positive or indeterminate on retest, the subject may not be randomized to IMP without further evaluation by a TB specialist and discussion with the Study Physician, if LTBI is identified. The retest must be done during the protocol-defined Screening window.
- Note: If available, respiratory or other specimens must also be smear and culture negative for TB (CDC diagnosis of LTBI) <http://www.cdc.gov/TB/topic/testing/default.htm>.
- f. NTMB infection is defined as a clinical infection caused by mycobacterial species other than those belonging to the *Mycobacterium tuberculosis* complex.
- g. Tuberculosis test conversion:
- A positive IGRA result for the current test when previous IGRA test results were negative. All subjects with TB test conversion must immediately stop IMP administration and be referred to a TB specialist for further evaluation. Confirmed TB test conversions should be classified as due to LTBI, active TB infection, or NTMB, and reported to the UCB PS function.

Subject eligibility, retesting requirements, and treatment requirements are depicted in [Figure 12-1](#).

